9.4 Study agreements

The Principal Investigator at each/the centre should comply with all the terms, conditions, and obligations of the Clinical Study Agreement, or equivalent, for this study. In the event of any inconsistency between this Clinical Study Protocol and the Clinical Study Agreement, the terms of Clinical Study Protocol shall prevail with respect to the conduct of the study and the treatment of patients and in all other respects, not relating to study conduct or treatment of patients, the terms of the Clinical Study Agreement shall prevail.

Agreements between AstraZeneca and the Principal Investigator should be in place before any study-related procedures can take place, or patients are enrolled.

Archiving of study documents

The investigator follows the principles outlined in the Clinical Study Agreement.

9.5 Study timetable and end of study

The end of the study is defined as 'the last visit of the last patient undergoing the study'.

The study is expected to start in Q2 2014 and to end by Q3 2017.

The study may be terminated at individual centres if the study procedures are not being performed according to GCP, or if recruitment is slow. AstraZeneca may also terminate the entire study prematurely if concerns for safety arise within this study or in any other study with MEDI4736.

The data cut-off for the final analysis of OS will take place approximately 12 months after the last patient is enrolled in each cohort. At this time point for the final cohort to be analysed, the clinical study database will be closed to new data. Patients who are receiving treatment can either choose to discontinue from the study or where the investigator believes patients are gaining clinical benefit, patients may continue to receive investigational product. All patients

will receive follow-up care in accordance with standard local clinical practice. For patients who do continue to receive treatment beyond the time of the final data cut-off, investigators will continue to report all SAEs to [redacted] until 90 days after investigational product is discontinued, in accordance with Section 6.4.4 (Reporting of Serious Adverse Events). Additionally as stated in Section 6.4.3 (Recording of adverse events), any SAE or non-serious AE that is ongoing at the time of this data cut-off must be followed up to resolution unless the event is considered by the investigator to be unlikely to resolve, or the patient is lost to follow-up.

10. DATA MANAGEMENT BY ASTRAZENECA OR DELEGATE

Data management will be performed by [redacted]

The data collected through third party sources will be obtained and reconciled against study data.

Adverse events and medical/surgical history will be classified according to the terminology of the latest version the Medical Dictionary for Regulatory Activities (MedDRA). Medications will be classified according to the AstraZeneca Drug Dictionary. All coding will be performed by [redacted]

Data queries will be raised for inconsistent, impossible or missing data. All entries to the study database will be available in an audit trail.

The data will be validated as defined in the Data Management Plan. Quality control procedures will be applied to each stage of data handling to ensure that all data are reliable and have been processed correctly.

When all data have been coded, validated, signed and locked, clean file will be declared. Any treatment revealing data may thereafter be added and the final database will be locked.

Data associated with biological samples will be transferred to laboratories internal or external to AstraZeneca/MedImmune.

Any genotype data generated in this study will be stored in the AstraZeneca genotyping Laboratory Information Management System (LIMS) database, or other appropriate secure system within AstraZeneca and/or third party contracted to work with AstraZeneca/MedImmune to analyse samples. The results from this genetic research may be reported in the CSR for the main study, or in a separate report as appropriate.

Some or all of the clinical datasets from the main study may be merged with the genetic data in a suitable secure environment separate from the clinical database.

11. EVALUATION AND CALCULATION OF VARIABLES BY ASTRAZENECA, OR DELEGATE

A comprehensive statistical analysis plan (SAP) will be prepared with additional details to support analyses specified in the protocol.

11.1 Calculation or derivation of efficacy variable(s)

11.1.1 RECIST 1.1 based endpoints

11.1.1.1 Independent Central Review of RECIST 1.1-based assessments

The ICR of all radiological imaging data will be carried out using RECIST version 1.1. All radiological scans for all patients (including those at unscheduled visits, or outside visit windows) will be provided to the ICR. Prior radiotherapy reports will also be provided to the ICR to allow the selection of appropriate target lesions. The imaging scans will be reviewed by 2 independent radiologists using RECIST 1.1 and will be adjudicated, if required. For each patient, the ICR will define the overall visit response data (CR, PR, SD, PD or not evaluable) and the relevant scan dates for each time point (ie, for visits where response or progression is/is not identified). If a patient has had a tumour assessment that cannot be evaluated then the patient will be assigned a visit response of not evaluable (unless there is evidence of progression in which case the response will be assigned as PD). All RECIST endpoints will be derived from the overall visit response date and the scan dates.

Further details of the ICR will be documented in the ICR Charter.

11.1.1.2 Investigator RECIST 1.1-based assessments

All RECIST assessments, whether scheduled or unscheduled, will be included in the calculations. This is also regardless of whether a patient discontinues study treatment or receives another anti-cancer therapy.

At each visit, patients will be programmatically assigned a RECIST 1.1 visit response of CR, PR, SD or PD depending on the status of their disease compared with baseline and previous assessments. Baseline will be assessed within the 28 days prior to randomisation. If a patient has had a tumour assessment that cannot be evaluated then the patient will be assigned a visit response of not evaluable (NE) (unless there is evidence of progression in which case the response will be assigned as PD).

Please refer to [Appendix F](#) for the definitions of CR, PR, SD and PD.

11.1.2 Independent Central Review of irRECIST 1.1-based assessments

To support an exploratory objective of response to therapy by irRC, the ICR of all radiological imaging data will also be carried out using irRECIST as outlined by ([Nishino et al 2013](#)).

The criteria that built the foundation for irRC were the WHO criteria which existed before the publication of RECIST 1.1. irRC are, therefore, like WHO criteria, based on bi-dimensional

measurements (Wolchok et al 2009). More recently RECIST 1.1 has become the gold standard for disease status determination in solid tumours. To be more in line with RECIST 1.1 criteria, irRC has been adjusted so that uni-dimensional measurements are used (referred to as irRECIST 1.1). This modification of irRC 2009 criteria (irRECIST 1.1) is suggested based on the results of Nishino et al 2013 who found that irRC using the uni-dimensional measurements provide highly concordant response assessment compared with the bi-dimensional irRC, with less measurement variability. Furthermore, this enables a consistency with RECIST 1.1 which enables a clearer contrast of the results from the two methods than would otherwise be possible.

The definitions of CR, PR, SD and PD according to irRECIST 1.1 will be outlined clearly in the ICR charter.

11.1.3 Objective response rate

The primary endpoint is ORR. ORR (per RECIST 1.1 as assessed by the ICR) is defined as the number (%) of patients with a confirmed overall response of CR or PR and will be based on a subset of all treated patients. If the ICR finds any patients do not have measurable disease at baseline then the analysis of ORR for the ICR data will exclude these patients, so that the denominator is a subset of all treated patients who have measurable disease at baseline per ICR. However, for Cohort 2, a sensitivity analysis will be performed where the analysis of ORR for the ICR data will include these patients (ie, based upon all treated patients with measurable disease at baseline per the site investigator).

A confirmed response of CR/PR means that a response of CR/PR is recorded at 1 visit and confirmed by repeat imaging not less than 4 weeks after the visit when the response was first observed with no evidence of progression between the initial and CR/PR confirmation visit. Therefore, data obtained up until progression, or the last evaluable assessment in the absence of progression, will be included in the assessment of ORR. Any patient who discontinues treatment without progression, receives a subsequent therapy and then responds will not be included as responders in the ORR.

ORR will also be obtained using the algorithm described above for the RECIST site investigator tumour data. The denominator for ORR will be all treated patients with measurable disease at baseline per the site investigator.

Additionally, ORR will be obtained using the algorithm described above from the RECIST ICR tumour data, but following a modification where any objective progression requires confirmation. Therefore, data obtained up until confirmed progression, or the last evaluable assessment in the absence of a confirmed progression, will be included in the assessment of ORR. Note that the response may be after an unconfirmed progression.

For exploratory purposes, ORR will also be obtained for the irRECIST 1.1 data obtained from ICR. Responses of CR/PR also need confirmation under this approach.

11.1.4 Duration of response

Duration of response (per RECIST 1.1 as assessed by the ICR) will be defined as the time from the date of first documented response (which is subsequently confirmed) until the first date of documented progression or death in the absence of disease progression. The end of response should coincide with the date of progression or death from any cause used for the RECIST 1.1 PFS endpoint (Section 11.1.7).

The time of the initial response will be defined as the latest of the dates contributing towards the first visit response of PR or CR that is subsequently confirmed.

If a patient does not progress following a response, then their DoR will be censored at the PFS censoring time.

Duration of response will not be defined for those patients who do not have confirmed response.

Duration of response will also be obtained using the algorithm described above for the RECIST site investigator tumour data.

For exploratory purposes, DoR will also be obtained using the irRECIST 1.1 data obtained from ICR. Both responses and disease progressions also need confirmation under this approach.

11.1.5 Disease control rate

The DCR at 6 months is defined as the percentage of patients who have a BoR of CR or PR in the first 6 months or who have demonstrated SD for a minimum interval of 24 weeks (-7 days, ie, 161 days) following the start of treatment. DCR at 12 months is defined as the percentage of patients who have a BoR of CR or PR in the first 12 months or who have demonstrated SD for a minimum interval of 48 weeks (-7 days, ie, 329 days) following the start of treatment.

Disease control rate will be determined programmatically based on RECIST using ICR data using all data up until the first progression event.

Disease control rate at other timepoints may also be analysed as appropriate.

Disease control rate will also be derived for the RECIST site investigator data.

For exploratory purposes, DCR will also be obtained using the irRECIST 1.1 data obtained from ICR. Disease progressions will need confirmation under this approach.

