11.1.7 Progression free survival

Progression free survival (per RECIST 1.1 as assessed by the ICR) will be defined as the time from the date of first dose until the date of objective disease progression or death (by any cause in the absence of progression) regardless of whether the patient withdraws from therapy or receives another anti-cancer therapy prior to progression. Patients who have not progressed or died at the time of analysis will be censored at the time of the latest date of assessment from their last evaluable RECIST 1.1 assessment. However, if the patient progresses or dies after 2 or more missed visits, the patient will be censored at the time of the latest evaluable RECIST 1.1 assessment. If the patient has no evaluable visits or does not have baseline data they will be censored at Day 1 unless they die within 2 visits of baseline.

The PFS time will always be derived based on scan/assessment dates not visit dates.

RECIST 1.1 assessments/scans contributing towards a particular visit may be performed on different dates. The following rules will be applied:

- Date of progression will be determined based on the earliest of the dates of the component that triggered the progression on the first set of scans that indicates progression.
- When censoring a patient for PFS the patient will be censored at the latest of the dates contributing to a particular overall visit assessment.

In the absence of clinically significant deterioration the investigational site is advised to continue the patient on MEDI4736 until progression has been confirmed.

For exploratory purposes, PFS will also be obtained using the irRECIST 1.1 data obtained from ICR. Objective disease progressions will require confirmation under this approach.

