12.2.2 Duration of response

Kaplan Meier plots of DoR based on the ICR assessment of RECIST will be presented for each cohort. Median DoR will also be summarised. Only patients who have a confirmed response will be included in this summary table. Duration of response will also be analysed based upon the site investigator tumour data.

The DoR will also be summarised using the irRECIST 1.1 data obtained from ICR.

Furthermore, DoR (using the programmatically derived DoR based on ICR assessments) may also be summarised by cohort for the PD-L1 negative patients in Cohort 1 and, additionally, for all patients in a combined population of Cohorts 1 and 2.

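### DCR and the confirmation of response have no cut-off at subsequent anti-cancer therapy, although ORR excludes responses that begin after it

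*Protocol*

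**What the plan says.** For ORR, Section 11.1.3 uses data up to progression and then adds an exclusion: "Any patient who discontinues treatment without progression, receives a subsequent therapy and then responds will not be included as responders in the ORR". In the same section a response is confirmed when it is "confirmed by repeat imaging not less than 4 weeks after the visit when the response was first observed with no evidence of progression between" the two visits. Nothing is said about therapy started between them.

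For DCR, Section 11.1.5 counts a best response of CR or PR, or a patient who has "demonstrated SD for a minimum interval of 24 weeks (-7 days, ie, 161 days) following the start of treatment"; the 12-month version uses 329 days. The data window is: "Disease control rate will be determined programmatically based on RECIST using ICR data using all data up until the first progression event". The ORR exclusion is not repeated.

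For DoR, Section 11.1.4 says "Duration of response will not be defined for those patients who do not have confirmed response", and Section 12.2.2 adds "Only patients who have a confirmed response will be included in this summary table". Section 11.1.6 limits TTR in the same way, and Section 12.2.4 bases its percentages on the number of responders. None of these refers to the ORR exclusion. The end of DoR follows PFS, which Section 11.1.7 measures "regardless of whether the patient withdraws from therapy or receives another anti-cancer therapy prior to progression".

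For investigator data, Section 11.1.1.2 includes all assessments and adds: "This is also regardless of whether a patient discontinues study treatment or receives another anti-cancer therapy".

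Section 6.3.1 keeps scanning patients who stop treatment or receive another cancer therapy before progression, so the relevant scans will exist.

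**The concern.** The protocol accepts for ORR that a response which begins on another drug says nothing about MEDI4736. Section 11.2.1 applies similar reasoning to safety, where the main adverse event summaries stop at the first subsequent therapy. DCR and the confirming scan do not follow that principle, and no reason is given for the difference.

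With no control arm, nothing offsets the effect of a later drug. Section 3.2 intends the study for a registration package and justifies ORR partly by the durability of responses. DCR could then include benefit produced by another agent. The confirmed ORR could include responses whose persistence was seen only on another agent. The responders described by DoR and TTR might also differ from those counted in ORR.

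**Working it through.** **Planned figures.** Section 12.3 plans 94 patients per cohort, of whom 80 have measurable disease per the ICR (94 × 0.85 = 79.9). The stated exact (Clopper-Pearson) 95% intervals reproduce: 20/80 gives 16.0% to 35.9%, and 32/80 gives 29.2% to 51.6%. The DCR limits also reproduce: 24 × 7 − 7 = 161 days and 48 × 7 − 7 = 329 days. None of these depends on the later-therapy rule.

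**Denominators.** Table 9 and Section 12.2 analyse DCR on the full analysis set, about 94 patients per cohort. Only the primary ORR analysis uses the subset of about 80.

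**The rules applied to three hypothetical patients**, each switching without progression:

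- *A: stable disease on MEDI4736; switches; PR at Week 16 and again at Week 24 on the new drug.* ORR: excluded by Section 11.1.3. DCR at 6 months: counted, because the PR falls before first progression. DoR and TTR: not expressly excluded, because the response is confirmed by imaging.
- *B: stable disease at Weeks 8 and 16; switches; stable at Week 24 on the new drug.* ORR: not a responder. DCR at 6 months: counted, because stable disease passes day 161.
- *C: first PR at Week 8 on MEDI4736; switches; still PR at Week 16 on the new drug.* ORR: counted as confirmed. The exclusion covers therapy followed by response, and here the response came first.

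**Size per patient.** DCR: 1/94 = 1.06 points. ORR: 1/80 = 1.25 points.

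**Size for k affected patients.** The protocol gives no number of switchers, so k is an assumption.

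- ORR, starting from the planned example of 20/80 = 25.0%: k = 1 gives 19/80 = 23.8% (14.9, 34.6); k = 2 gives 18/80 = 22.5% (13.9, 33.2); k = 4 gives 16/80 = 20.0% (11.9, 30.4).
- DCR, starting from an assumed 38/94 = 40.4% (30.4, 51.0): k = 2 gives 36/94 = 38.3% (28.5, 48.9); k = 4 gives 34/94 = 36.2% (26.5, 46.7); k = 6 gives 32/94 = 34.0% (24.6, 44.5).
- DoR and TTR, if k patients like A joined 20 ORR responders: k = 1 is 1/21 = 4.8% of the set; k = 4 is 4/24 = 16.7%.

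**What the protocol offers on plausible k.** Section 1.1.3.2 reports that drug-related adverse events led to discontinuation in 1% of 190 NSCLC patients in Study 1108. That is 0.01 × 94 = 0.9 patients per cohort from this cause. It is not an upper limit, since patients also stop for symptomatic deterioration or by choice. Section 1.1.1 puts response to further systemic treatment in refractory disease below 10%, which suggests that stable disease (patient B) is a likelier route into DCR than a new response (patient A).

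**The case against.** The strongest case against is that most of this is either deliberate or narrow, and much of it stands.

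- *The exposed group is small.* Patients who stop after confirmed progression have only optional scans, which end when new treatment starts, and the primary RECIST derivations stop at first progression. Only those who switch before progression matter. This stands.
- *A response confirmed after a switch may still be a MEDI4736 response.* It was first seen on MEDI4736, and Section 3.2 describes immune responses that persist after treatment stops. A strict rule would reject some true responses. This stands, and is why a sensitivity analysis is an acceptable alternative for ORR.
- *Details may sit in the SAP.* The SAP was not available, and Section 11.1 gives no derivation of best response. But the DCR data window and the confirmation rule are fixed in the protocol, and they differ from the ORR rule.

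Several stronger readings are tempting but unsupported:

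- A reader might infer that the trial's results in general credit MEDI4736 with later treatment. They do not: Section 11.1.3 removes first responses on later therapy from the primary endpoint.
- A reader might infer that ORR non-responders enter DoR and TTR. The text leaves the responder set unclear; it does not state their inclusion. Sections 12.2.2 and 12.2.4 can be read as meaning the ORR responders.
- A reader might call it an error that DoR runs on through other therapy. It is a declared choice, consistent with PFS.
- A reader might attach a total of several points to the DCR effect. That needs a switching rate which the protocol does not give, and it requires every switcher to be counted only because of the new drug.

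**Conclusion.** The inconsistency between ORR and DCR is plain in the text, and the confirmation rule leaves a gap that reaches the primary endpoint. The link between DoR, TTR and the ORR responders needs stating, but is no more than unclear.

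The effect is about 1.1 points of DCR or 1.25 points of ORR per affected patient, assuming about 94 patients in the full analysis set and 80 with measurable disease per the ICR. The total cannot be established from the protocol. The direction is known: for a given set of scans, each gap can only raise DCR or confirmed ORR. No hypothesis is tested, and the planned sample size and intervals do not change. The correction should be made because the endpoints are read without a comparator.

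**What to change.** - **Section 11.1.5:** derive DCR from ICR scans up to the earlier of first progression and the start of subsequent anti-cancer therapy, for both the CR/PR and the stable disease components.
- **Section 11.1.3:** require the confirming scan to precede subsequent therapy, or keep the present rule and report ORR with that requirement as a sensitivity analysis.
- **Sections 11.1.4 and 11.1.6:** state that DoR and TTR are defined for the patients counted as responders in ORR.
- **Investigator-based analyses:** apply the same rules, and align the general statement in Section 11.1.1.2 with them.
- **Leave PFS and the primary DoR as defined.** A DoR sensitivity analysis censored at the last evaluable scan before subsequent therapy is optional.

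The cost is wording and programming. Tables 2 and 3 already collect subsequent anti-cancer therapy, and no extra scans are needed. The downside is that DCR and confirmed ORR may be slightly lower, and a true MEDI4736 response confirmed only after a switch would not count under the strict rule.

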11.1.6 Time to response

Time to response (per RECIST 1.1 as assessed by the ICR) is defined as the time from the date of first dose until the date of first documented response (which is subsequently confirmed). The date of first documented response should coincide with that used for the RECIST 1.1 DoR endpoint.

Time to response will not be defined for those patients who do not have confirmed response. Time to response will also be derived for the RECIST site investigator data.

For exploratory purposes, TTR will also be obtained using the irRECIST 1.1 data obtained from ICR. Disease progressions will need confirmation under this approach.

